6.5 Multiplicity Control

To control the overall type I error at 0.05 level for the study, a hierarchical testing strategy will be applied to test the four null hypotheses defined in [Section 4.2](#) in the following order.

Step 1: Test null hypotheses H_0^1 and H_0^2 at 2-sided 0.025 level respectively.

If both null hypotheses H_0^1 and H_0^2 in Step 1 are rejected, the following steps will be performed at a two-sided $\alpha_1=5\%$ level. If only null hypothesis H_0^1 is rejected, the following steps will be performed at a two-sided $\alpha_1=2.5\%$ level.

Step 2: Test null hypothesis H_0^3 at α_1 level, if at least null hypothesis H_0^1 in Step 1 is rejected.

Step 3: Test null hypothesis H_0^4 at α_1 level, if the null hypotheses in Step 1 and Step 2 are all rejected.

Step 4: Test null hypothesis H_0^5 at α_1 level, if the null hypotheses in Step 1, Step 2, and Step 3 are all rejected.

The testing sequence can only continue to the next step if all prior steps achieve statistical significance at the specified α_1 level (per Step 1). If a step fails to demonstrate statistical significance at the specified α_1 level (per Step 1), then the testing sequence will stop, and all steps thereafter will not be conducted. Detailed descriptions are presented in Section 9.2 and Section 9.6.2 in Protocol Amendment 2.

All other endpoints are not controlled for multiplicity and the analyses are descriptive in nature.

The study success can only be declared if non-inferiority of mRNA-1010 vs. active comparator is demonstrated for both A strains and B strains on GMT ratio and SCR.

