9.6.2 Multiplicity

To control the overall Type I error for the study, a hierarchical testing strategy will be used to test the primary and secondary immunogenicity objectives (Figure 1).

Figure 1: Testing Sequence of the Primary and Secondary Objectives

At the first step in the testing sequence as demonstrated in [Figure 1](#), the noninferiority of mRNA-1010 compared with active comparator for A strains and for B strains will be tested at a type I error rate of 2.5% (2-sided) respectively.

If noninferiority is demonstrated for A strains only at the first step, the superiority testing for A strains will be tested following the order of testing sequence at a type I error rate of 2.5% (2-sided).

If non-inferiority is demonstrated for both A and B strains at the first step, the type I error rate for the following test will be 5% (2-sided).

The testing sequence can only continue to the next level if the tests at the higher level meet the success criteria (as specified in [Section 9.2](#)). If a test at the higher level fails to meet the success criteria for that level, the testing sequence will stop, and all testing thereafter will not be conducted.

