The study success can only be declared if the success criteria of the non-inferiority for both A strains and B strains are met.

Once the non-inferiority success criteria of the co-primary endpoints for A strains are met, hypothesis testing will continue (sequentially) based on α_1 as defined below to support secondary objectives, as follows.

Hypotheses in support of the secondary objectives will be tested at a two-sided $\alpha_1=5\%$ level if non-inferiority is demonstrated for both A and B strains (both H^1_0 and H^2_0 are rejected), and at an $\alpha_1=2.5\%$ level if non-inferiority is only demonstrated for A strains (only H^1_0 is rejected).

The null hypothesis H^3_0 : immunogenicity response to mRNA-1010 compared to that in participants who received the active comparator, as measured by GMR at Day 29 using HAI assay, is ≥ 1 for each individual A strain (H1N1 and H3N2). The superiority success criteria in immunogenicity response are met if H^3_0 is rejected at two-sided α_1 level. Based on GMT, superiority will be demonstrated by the lower bound of the $(100\% - \alpha_1)$ CI of the GMR ruling out 1 (lower bound > 1) for both A strains.

Once the success criteria of hypothesis H^3_0 are met, the next null hypothesis to be tested is H^4_0 .

The null hypothesis, H^4_0 : immunogenicity response to mRNA-1010 compared to that in participants who received the active comparator, as measured by GMR at Day 29 using HAI assay, is ≥ 1.5 for each individual A strain (H1N1 and H3N2). The super-superiority success criteria in immunogenicity response are met if H^4_0 is rejected at two-

sided α_1 level. Based on in GMT, super-superiority will be demonstrated by the lower bound of the $(100\% - \alpha_1)$ CI of the GMR ruling out 1.5 (lower bound > 1.5) for both A strains.

Once the success criteria of hypothesis H^4_0 are met, the last null hypothesis to be tested is H^5_0 .

The null hypothesis, H^5_0 : immunogenicity response to mRNA-1010 compared to that in participants who received the active comparator, as measured by SCR difference at Day 29 using HAI assay, is not super-superior for each individual A strain (H1N1 and H3N2). The super-superiority success criteria based on SCR are met if H^5_0 is rejected at two-sided α_1 level. Based on SCR, super-superiority will be demonstrated by the lower bound of the $(100\% - \alpha_1)$ CI of the SCR difference ruling out 10% (lower bound $> 10\%$) for both A strains.

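### The testing sequence omits two valid alpha transfers, from the B-strain to the A-strain non-inferiority test and from a completed A branch back to the B strains; adding them is a free improvement, worth nothing under the planning assumptions

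*SAP*

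**What the plan says.** SAP 6.5 sets out a hierarchical procedure "To control the overall type I error at 0.05 level for the study". H1 (A strains) and H2 (B strains) are non-inferiority families of four endpoints each, and all four must be met. Both are tested first, "at 2-sided 0.025 level respectively".

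Three further A-strain hypotheses follow in order: H3 (GMR above 1), H4 (GMR above 1.5) and H5 (seroconversion difference above 10 points). SAP 4.2, 6.3.2 and 6.5 and Protocol 9.2 and 9.6.2 all set their level at 5% if H1 and H2 are both rejected. Protocol 9.6.2 also gives the A-only path: "If noninferiority is demonstrated for A strains only at the first step, the superiority testing for A strains will be tested following the order", at 2.5%.

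On failure, SAP 6.5 says "then the testing sequence will stop, and all steps thereafter will not be conducted", and Protocol 9.6.2 says "the testing sequence will stop, and all testing thereafter will not be conducted". Neither document has a rule that returns to H1 or H2 after Step 1.

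SAP 4.2 adds: "The study success can only be declared if the success criteria of the non-inferiority for both A strains and B strains are met". SAP 6.5 repeats this. SAP 6.5 also makes Steps 3 and 4 (H4 and H5) conditional on rejection of all the null hypotheses in Step 1, not of H1 alone.

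**The concern.** Bonferroni-based sequential testing allows a rejected hypothesis to hand its alpha to one not yet rejected. The plan uses this once: when H1 and H2 are both rejected, H2's 2.5% joins H1's and H3 to H5 run at 5%. It does not use it in two other places where it would be equally valid:

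- **(a)** H2 is rejected and H1 is not. H2's 2.5% is not passed to H1.
- **(b)** H1, H3, H4 and H5 are all rejected at 2.5% and H2 is not. The A branch's 2.5% is not passed back to H2.

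Both omissions bear on the headline result, because success needs H1 and H2 together. Suppose every B endpoint passes at 2.5% and the weakest A endpoint has a two-sided p-value between 2.5% and 5%. The plan then records a failed study, where a procedure with the same 5% error rate would record success.

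**Working it through.** **1. The plan's own power figure.** Inputs from SAP 4.3: 6000 × 0.85 = 5100, or 2550 per arm; SD of ln titer 1.5; GMR 0.9; seroconversion 70% (A) and 60% (B) with true difference 0; margins 1.5 and 10 points. The critical value is 2.241 for two-sided 2.5% and 1.960 for 5%.

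- GMT: SE = 1.5 × √(2/2550) = 0.0420. Distance to the margin = ln(0.9 × 1.5) = 0.3001, or 7.14 SE. Power per strain = Φ(7.14 − 2.24) = 0.9999995; for all four strains, if independent, 0.999998.
- Seroconversion: SE = √(2 × 0.7 × 0.3/2550) = 0.0128 for A and √(2 × 0.6 × 0.4/2550) = 0.0137 for B. Power exceeds 0.9999997 per strain; for all four, 0.9999995.

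The stated power of at least 95% is reproduced and far exceeded.

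**2. Where alpha goes, by Step 1 result.**

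| Step 1 result | What the plan does | Unused alpha |
|---|---|---|
| H1 and H2 rejected | H3 to H5 at 5% | none |
| H1 only | H3 to H5 at 2.5% | 2.5% if all three are rejected (outcome b) |
| H2 only | stop | 2.5% (outcome a) |
| Neither | stop | nothing available to pass |

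**3. Error control with both transfers added.** If H1 and H2 are both true nulls, the first false rejection must occur at 2.5% + 2.5% = 5%. If only one is true, it is tested at no more than 5%. If H1 is false but a later A hypothesis and H2 are true, each still holds 2.5% until the other is rejected. Every rejection in the current plan remains a rejection.

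**4. Largest possible gain when one family is marginal and the other secure.** The gain is Φ(m − 1.960)^k − Φ(m − 2.241)^k, where k independent endpoints each lie m SE from the margin.

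- k = 1: power rises from 44.4% to 55.6%, a gain of 11.2 points.
- k = 2: 41.3% to 55.0%, a gain of 13.6 points.
- k = 4: 38.4% to 54.6%, a gain of 16.2 points.

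Worked case for k = 2, with GMR 0.74 in both A strains: ln(0.74 × 1.5)/0.0420 = 2.48. Then Φ(0.24)² = 0.355 and Φ(0.52)² = 0.490. Simulation gives 35.4% and 48.9%. With between-strain correlation 0.5 it gives 43.5% and 55.6%.

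**5. Simulated probability of study success.** 400,000 runs per scenario. The documents give no correlations; this table assumes 0.3 between strains and 0.5 between GMT and seroconversion within a strain. The seroconversion difference is 0 unless shown.

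| True effects | Plan | With both transfers | Gain (points) |
|---|---|---|---|
| A GMR 0.78, SCR −3 points; B 0.9 | 87.6% | 92.9% | 5.3 |
| All strains 0.75 | 36.1% | 42.2% | 6.1 |
| A 0.75; B 0.9 | 54.6% | 66.8% | 12.2 |
| A 0.74; B 0.9 | 40.2% | 52.9% | 12.7 |
| A 1.9, SCR +17; B 0.75 | 54.5% | 66.7% | 12.2 |
| A 1.9, SCR +17; B 0.74, SCR −5 | 37.8% | 50.9% | 13.1 |

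Under the planning assumptions success is 0.999998 with or without the transfers; even testing all eight endpoints at 5% adds only 0.0002 points. With A at GMR 1.1 and B at 0.75 the gain is zero, because H4 and H5 are not rejected and outcome (b) does not arise.

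**6. SAP Steps 3 and 4.** Read literally, they require H2 as well as H1 to be rejected before H4 or H5 is tested. Outcome (b) could then never occur. That reading conflicts with the A-only path at 2.5% in SAP 4.2, in Protocol 9.6.2 and earlier in SAP 6.5 itself. The two must be reconciled before a return to H2 can operate.

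**The case against.** The strongest reply is that the plan makes no error. It is a valid, conservative procedure, its power statement reproduces, and the existence of a more powerful valid procedure is not in itself a defect. The gain appears only when true GMRs fall to about 0.74 to 0.78, or seroconversion differences to about −6.5 points, far from the planning values. The return to H2 also needs A strains near GMR 1.9 or 2.0 while B is marginal. Protocol Amendment 2 revised the hypotheses and sequence in response to regulatory comments, and allowing a primary family to be won at 5% changes the primary success rule.

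All of that stands as a limit on the size and status of the point. It does not make the change a trade-off: both transfers keep the 5% error rate and can never lose a rejection. The amendment summary ties the revision to superiority testing; it does not say that regulators asked for these transfers to be left out.

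A reader might go further and infer that the plan never passes B-strain alpha to the A strains, or that half the 5% is always stranded. The documents do not support either. H3 to H5 rise to 5% when both families succeed, and Step 1 allocates the full 5%. Alpha goes unused only in outcomes (a) and (b).

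**Conclusion.** Two valid alpha transfers are missing: from H2 to H1 when only H2 is rejected, and from the completed A branch to H2. This is a free improvement, not a validity error.

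The loss in success probability is zero under the planning assumptions, about 5 to 13 points in the near-margin scenarios simulated, and about 11 to 16 points at worst. The worst case depends on how many endpoints are marginal and on correlations that had to be assumed. A figure of 13 points should therefore not be read as a loss under the design; it belongs to true effects close to the margin. The benefit is insurance against one family falling well short of its planning value.

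**What to change.** Before unblinding for the primary analysis, amend SAP 6.5 and Protocol 9.2 and 9.6.2:

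1. If H2 is rejected at two-sided 2.5% and H1 is not, retest H1 at two-sided 5%. If it is then rejected, continue to H3, H4 and H5 at 5%.
2. If H1, H3, H4 and H5 are all rejected at two-sided 2.5% and H2 is not, retest H2 at two-sided 5%.
3. Reword SAP Steps 3 and 4 to require rejection of H1 and of the preceding steps, not of every Step 1 null. This matches the A-only path in SAP 4.2 and Protocol 9.6.2, and step 2 cannot operate without it. In the same edit, correct the count in SAP 6.5, which refers to four null hypotheses where SAP 4.2 lists five.
4. Report 95% CIs beside the 97.5% CIs for the non-inferiority endpoints, so that a retest at 5% can be read from the tables.

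The cost is wording and a slightly longer description: no extra participants and no loss of error control. Because steps 1 and 2 change the primary success rule, they belong in the protocol as well as the SAP, whose introduction confines its own changes to matters that are not principal. Step 3 is needed even if steps 1 and 2 are declined.

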6.6 Safety Analysis

Safety and reactogenicity will be assessed by clinical review of all relevant parameters, including solicited ARs (local and systemic events), unsolicited AEs, SAEs, fatal events, AESIs, MAAEs, AEs leading to withdrawal from study participation. Solicited ARs and unsolicited AEs will be

coded by SOC and PT according to the MedDRA version 25.0 or higher. All safety endpoints will be summarized by vaccination group corresponding to actual IP they received for the Safety Set, except summaries of solicited ARs, which will be based on the Solicited Safety Set.

When summarizing the number and percentage of participants with an event, participants with multiple occurrences of the same AE/AR or a continuing AE/AR will be counted once. Participants will be presented according to the highest severity/toxicity in the summaries by severity/toxicity, if participants reported multiple events under the same SOC and/or PT. SOC will be displayed in an internationally agreed order. PT will be displayed in descending order of frequency of mRNA-1010 vaccination group within each SOC.

6.6.1 Analysis of Solicited Adverse Reactions

An AR is defined as any AE for which there is a reasonable possibility that the IP may have caused the AE. The term “Solicited Adverse Reaction” refers to selected signs and symptoms occurring after IP injection during a specified post-injection follow-up period (day of injection and 6 subsequent days).

The solicited ARs are recorded by the participant in the eDiary. The eDiary will solicit daily participant reporting of occurrence and intensity of ARs using a structured checklist from Day 1 through 7 days after the IP injection (i.e., the day of injection and 6 subsequent days). Any solicited ARs started during the 7-day follow-up period post-injection, if not reported in the eDiary, should be entered on the Reactogenicity eCRF and will be included in the evaluation of solicited ARs in addition to the eDiary.

If a solicited local or systemic AR starts on or after Day 8, it should be captured on the AE eCRF page until no longer reported.

Any solicited AR that meets any of the following criteria must be entered into the participant’s source document and must be recorded in the participant’s Reactogenicity eCRF:

- Solicited local or systemic AR that results in a visit to a healthcare practitioner
- Solicited local or systemic AR leading to the participant withdrawing from the study or the participant being withdrawn from the study by the investigator (AE leading to withdrawal)
- Solicited local or systemic AR continuing beyond 7 days post-injection
- Solicited local or systemic AR that otherwise meets the definition of an SAE

The following local ARs will be solicited by the eDiary: injection site pain, injection site erythema (redness), injection site swelling/induration (hardness), and axillary swelling or tenderness ipsilateral to the side of injection.

The following systemic ARs will be solicited by the eDiary: headache, fatigue, myalgia, arthralgia, nausea/vomiting, chills, and fever (oral).

The solicited ARs will be graded based on the grading scales presented in the protocol, modified from the Toxicity Grading Scale for Healthy Adult and Adolescent Volunteers Enrolled in Preventative Vaccine Clinical Trials (DHHS 2007b) in [Section 9.6](#). Grading of Grade 4 events will be determined per investigator and assessment is recorded on the reactogenicity event page in the eCRF .

Analyses of solicited ARs will be provided by vaccination group based on the Solicited Safety Set, unless otherwise specified. All solicited ARs (overall, local, and systemic) reported during the 7-day follow-up period after injection will be summarized. The number and percentage along with its 2-sided 95% exact CI (using the Clopper-Pearson method) of participants with any solicited local AR, solicited systemic AR, and solicited AR during the 7-day follow-up period after the injection will be provided. The same analysis will be conducted for subgroups defined by age group1, age group 2, race, and sex (see [Table 5](#)).

The number and percentage of participants who reported each individual solicited local AR (has a toxicity grade of Grade 1 or greater) and solicited systemic AR (has a severity grade of Grade 1 or greater) during the 7-day follow-up period after injection will be provided by toxicity grade. The same analysis will be conducted for subgroups defined by age group1, age group 2, race, and sex (see [Table 5](#)).

The number and percentage of participants with onset of individual solicited AR will be summarized by study day relative to the injection (Day 1 through Day 7). The onset of individual solicited AR is defined as the time point after injection at which the respective solicited AR first occurred.

Descriptive statistics will be provided for the duration of solicited ARs (overall, local, and systemic) and each individual SAR by vaccine group. The duration of local or systemic solicited ARs, along with the specific individual solicited ARs, will be calculated as: reaction end date –

reaction start date +1, no matter it is intermittent or continued or if the solicited AR continues beyond 7 days.

All solicited ARs that continue beyond 7 days post-injection will be summarized. All delayed ARs with onset day after 7 days post-injection will also be summarized.

Solicited local and systemic ARs will be provided in a listing. All solicited ARs that continue beyond 7 days post-injection will be listed as well.

6.6.2 Unsolicited Treatment-Emergent AEs

A treatment-emergent AE (TEAE) is defined as any event occurring during the study not present before exposure to IP or any event already present that worsens in intensity or frequency after exposure to IP. Worsening of a pre-existing condition after vaccination will be reported as a new AE.

AEs will also be evaluated by the investigator for the coexistence of MAAE and/or AESI. An MAAE is an AE that leads to an unscheduled or scheduled visit to a healthcare practitioner. AESIs for this study are pre-defined in the protocol appendix 3 including thrombocytopenia, neurologic diseases, anaphylaxis, and myocarditis/pericarditis.

Unsolicited AEs will be collected from Day 1 through 28 days after the IP injection on the AE page and reactogenicity page of the eCRF. SAEs, MAAEs, AESIs and AEs leading to withdrawal will be collected from Day 1 until the end of participation in the study. Analyses of unsolicited AE will be provided for up to 28 days after vaccination unless otherwise specified.

All summary tables (except for the overall summary of AEs) for unsolicited AEs will be presented by SOC and PT or by PT only for TEAEs with counts of participants included. SOC will be displayed in internationally agreed order. PTs will be displayed in descending order of frequency in the mRNA-1010 group and then alphabetically within SOC. When summarizing the number and percentage of participants with an event, participants with multiple occurrences of the same AE or a continuing AE will be counted once. Only the maximum severity level will be presented in the severity summaries, and the strongest relationship level will be presented in the relationship summaries.

Unsolicited TEAEs will be summarized up to 28 days after vaccine injection. Treatment emergent SAEs, MAAEs, AESIs and AEs leading to withdrawal will be summarized for up to 180 days after vaccine injection and throughout the study (up to Day 361 (Month 12)/EoS).

In addition, number of participants with occurrences of selected TEAEs of clinical interests identified by SMQ will be summarized. SMQ will be summarized by PT, if applicable. Detailed description of SMQ is presented in [Table 13](#) and [Table 14](#)

6.6.2.1 Overview of Unsolicited TEAEs

An overall summary of unsolicited TEAEs up to 28 days after IP injection (or other time frames, as applicable) including the number and percentage of participants who experienced the following will be presented:

- Any unsolicited TEAEs
- Any unsolicited treatment-related TEAEs
- Any serious TEAEs
- Any treatment-related serious TEAEs
- Any unsolicited severe TEAEs
- Any unsolicited treatment-related severe TEAEs
- Any unsolicited medically attended TEAEs
- Any unsolicited treatment-related medically attended TEAEs
- Any unsolicited treatment emergent AESI
- Any unsolicited TEAEs leading to discontinuation from participation in the study.

Listings containing individual participant AE data for unsolicited AEs, unsolicited AEs leading to discontinuation from participation in the study, SAEs, AESI, MAAEs will be provided separately.

